12.5.3.2 Response Evaluation and Reporting of Results

Response evaluation will be performed by external medical experts in relevant cancer types in collaboration with the sponsor Medical Officer and a Statistician.

Each patient will be assigned one of the following categories:

- 1) CR
- 2) PR
- 3) SD
- 4) PD or
- 5) Not Evaluable

Patients in response categories 1 and 2 are considered responders and patients in response categories 4 and 5 are considered as failing to respond to treatment (disease progression). Patients in response categories 1, 2 and 3 are considered to be in disease control.

Final 5.0 (incorporating Protocol Amendment 4)

Individual patient data listings and summaries of objective response, best overall tumor response and disease control will be presented by dose cohort and total. For respective patients, PSA (CRPC) and CA125 (ovarian and endometrial) will be listed.

The maximal response (maximal change in the sum of the LD in the target lesions) in target lesions at any time on trial will be reported using waterfall plots.

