7.2.2 Secondary Endpoints

- Safety laboratory parameters (hematology, biochemistry, coagulation factors and flow cytometry)
- Skin disorders
- Bleeding events
- Neuropathy
- PK parameters (clearance, volume of distribution and AUC [AUC0-Clast and AUC0-∞], Cmax, time of Cmax [Tmax], pre-dose values, and half-life of tisotumab vedotin (HuMax-TF-ADC) and free toxin [MMAE])
- Immunogenicity of tisotumab vedotin (HuMax-TF-ADC) (human anti-human antibodies)
- Anti-tumor activity measured by tumor shrinkage (based on CT-scan evaluations), change in PSA and CA 125
- Objective Response (Complete Response [CR] or PR), Disease Control (CR, PR or SD), Progression-Free Survival (PFS) and Duration of Response (DoR)

Final 5.0 (incorporating Protocol Amendment 4) 06 Jul 2017

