8.4.5 Dose Modification and Mitigation Plans

Dose modifications should be preapproved by the sponsor Medical Officer. Below the dose modification and mitigation plans are specified according to the once q3wk treatment scheme:

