8.4.9.5 Assignment to Treatment

This is an open-label trial. Trial participation begins once written informed consent is obtained.

After obtaining informed consent, patients will be given a screening number before they undergo any screening procedure. A screening number consists of the letter "S" followed by the trial number and subsequently a 3- or 4-digit number that uniquely identifies a patient at a Screening Visit. For example, a screening number in this trial could be "S702034".

Patients who have complied with all selection criteria will receive a patient number upon enrollment in the trial. A patient number consists of the trial number combined with a 3- or 4-digit number that uniquely identifies a patient during the trial. For example, patient 12 in this trial would be uniquely identified by the combined code "702012".

A master log of all consented patients will be maintained at the sites and will document all screening failures (i.e., patients who are consented but do not meet the trial eligibility criteria) including the reason for screening failure.

Final 5.0 (incorporating Protocol Amendment 4) 06 Jul 2017

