10.7 Computerized Tomography

All patients will have a CT-scan with contrast of thorax, abdomen and pelvis performed during screening. If there is suggestion of brain metastases/tumors, a CT-scan of the head will be performed before inclusion.

Up to five target lesions (maximum two per organ) will be defined at screening and these must be followed throughout the trial. Non-target lesions will also be assessed throughout the trial.

Final 5.0 (incorporating Protocol Amendment 4) 06 Jul 2017

Scans will be repeated every six weeks (at the end of every second cycle) during the trial period. If the result is PR or better, CT-scan should be repeated after four weeks to confirm response. CT-scans can be performed up to seven days before Day 1 of the relevant cycle to ensure results are available before subsequent dosing.

Additional CT-scans may be performed at the investigators' discretion to confirm response or new symptoms. In this case, the investigator must choose the imaging technology based on the clinical indication.

Magnetic resonance imaging can be performed instead of a CT-scan if the patient is allergic to iodine contrast or at the discretion of the investigator, after approval of the sponsor.

The reading of the surveys will be done by a radiologist. Sites should attempt to maintain the same radiologist throughout the trial. The overall interpretation of the evaluation shall be recorded in the eCRF and a copy of the evaluation reports should be kept in the patient's file.

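### The sponsor Medical Officer takes part, with no stated limit, in assigning each patient's response category in an open-label, uncontrolled trial

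*Protocol*

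**What the plan says.** Protocol 12.5.3.2 names who evaluates response: "Response evaluation will be performed by external medical experts in relevant cancer types in collaboration with the sponsor Medical Officer and a Statistician". It continues, "Each patient will be assigned one of the following categories", and lists CR, PR, SD, PD and Not Evaluable. The first two categories make a patient a responder. For disease control the rule is: "Patients in response categories 1, 2 and 3 are considered to be in disease control".

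There is a separate reading upstream. Section 10.7 says: "The reading of the surveys will be done by a radiologist. Sites should attempt to maintain the same radiologist throughout the trial". The overall interpretation goes into the eCRF.

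On the Medical Officer's other duties, 8.4.5 says: "Dose modifications should be preapproved by the sponsor Medical Officer". The officer also agrees discretionary dose reductions (8.1), judges whether certain events call for urgent DMC review (8.2.1), and attends the bi-weekly meetings on adverse events and laboratory data (11.6).

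Section 8.4.9.5 states: "This is an open-label trial". No part of the trial has a control arm.

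**The concern.** In an uncontrolled open-label trial, nothing cancels out a tendency to read borderline scans one way. External experts are a natural safeguard, and the protocol already provides them. It then brings into the same step a sponsor officer who knows each patient's dosing and toxicity, without saying whether that officer supplies data, advises or shares in the decision.

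The step leaves room for judgment. Under 12.5.3.1, CR and PR need no formal confirmation to count, and progression in non-target lesions rests on a judgment that it is unequivocal. Section 12.5.3 allows disease-specific guidelines as an alternative to RECIST. The SD/PR border decides objective response. The borders of SD with PD and with Not Evaluable decide disease control.

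Anti-tumor activity is a secondary objective (7.1.2), and the expansion part is meant to yield preliminary efficacy data (12.9). A reader of those results would want to know that the sponsor had no say in the individual calls.

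**Working it through.** The protocol gives no target response rate, power or event count for these endpoints, so there is no figure of its own to reproduce. The check is first a comparison of sections and then a calculation of scale.

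**Which endpoints depend on the joint step**

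| Endpoint | Source in the protocol | Link to the joint step |
|---|---|---|
| Objective response | 12.5.3.2, categories 1 and 2 | Direct |
| Disease control | 12.5.3.2, categories 1 to 3 | Direct |
| PFS | 12.5.3.3, Cycle 1 Day 1 to first PD or death | Not stated whose PD counts |
| DoR | 12.5.3.4, first documented response to first PD or death | Not stated whose PD counts |
| Adverse events (primary) | 12.4 | None |

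**Whether another section limits the officer's part.** None does. Section 10.7 provides a radiologist's reading and mentions neither a central nor a blinded read. Section 12.3 says that response rate gets an exact interval and that no tests are done; it does not say whose assessment is used. No section states how disagreement is settled, either between the officer and the experts or between the joint evaluation and the site reading.

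**Scale of a single call**

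Inputs: 20 to 30 expansion patients in two or three indication arms (8.3), with expansion tables reported by indication (12.3). An even split is my assumption.

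- Smallest arm: 20/3 = 6.7, about 7 patients.
- Largest arm: 30/2 = 15 patients.
- Shift in ORR from moving one patient between SD and PR = 1/n.

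| n | 1/n, percentage points |
|---|---|
| 7 | 14.3 |
| 10 | 10.0 |
| 15 | 6.7 |
| 20 (whole expansion, minimum) | 5.0 |
| 30 (whole expansion, maximum) | 3.3 |

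Exact (Clopper-Pearson) 95% limits for x responders out of n are the 0.025 quantile of Beta(x, n−x+1) and the 0.975 quantile of Beta(x+1, n−x). The responder counts below are assumed, for illustration only:

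- n = 10: 2 responders give 20.0% (2.5 to 55.6); 3 give 30.0% (6.7 to 65.2).
- n = 30: 5 responders give 16.7% (5.6 to 34.7); 6 give 20.0% (7.7 to 38.6).

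One call visibly moves an arm-level rate. These intervals describe sampling error; they do not allow for error in how patients were classified.

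**The case against.** The other side has real weight.

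- **The external experts perform the evaluation.** The sentence gives the sponsor no vote, veto or override. A reader might infer that independent review has been removed. The text does not go that far: independence is weakened because the officer's role is open-ended.
- **Safeguards exist.** Categories follow RECIST 1.1 thresholds and a combination table (12.5.3.1). A repeat CT is planned after a response. Individual response listings and waterfall plots are required (12.5.3.2), and all data are to be listed (12.3). These narrow the room for judgment and make the calls partly traceable. They do not say who decides a borderline case.
- **The Statistician may not be sponsor staff.** No affiliation is given, so only the Medical Officer is identifiably the sponsor's. It would be wrong to describe both as sponsor employees.
- **Bias in PFS is not established.** It is tempting to argue that a patient withdrawn on the site's PD, and not confirmed as PD in the joint evaluation, ends up censored. The protocol states neither a censoring rule nor which PD date is used, so this cannot be asserted.
- **The 1/n shift is the same whoever makes the call.** It reflects small arms. The two intervals at n = 10 overlap almost entirely.
- **Pre-approving dose changes shows knowledge of the patient's management,** not influence on a response call.
- **The consequence is limited.** This is a safety trial with adverse events as primary endpoint, no formal tests and no decision rule tied to ORR.

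Together these points lower the severity. They leave standing that a sponsor officer has an unlimited part in a step that directly produces two endpoints, and that the protocol itself fixes this. An SAP that excluded the officer would depart from 12.5.3.2.

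**Conclusion.** The point holds for objective response and disease control: 12.5.3.2 exposes both to avoidable sponsor influence at borderline calls. For PFS and DoR the exposure is possible but not shown, and the defect that can be stated there is that the source of the PD date is not named.

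As to size, one reclassified patient is worth about 7 to 14 percentage points of an arm's ORR at 15 down to 7 patients, given an even split. The documents offer no basis for estimating how often a call would actually change, so this must not be quoted as an amount of bias.

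The endpoints are secondary and descriptive, and the primary endpoint is unaffected. The change is worth making because it is cheap and because the experts it relies on are already planned.

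**What to change.** Amend 12.5.3.2 in three respects:

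1. The external experts alone decide each patient's response category and date of progression. The sponsor Medical Officer and the Statistician supply the data and program the results, with no say in the category or date.
2. This assessment is the source for ORR, disease control, PFS and DoR. Cross-refer to it from 12.5.3.3 and 12.5.3.4 so that the PD date has one named origin.
3. The site assessment already recorded under 10.7 is tabulated beside it, with the number of discordant patients, and ORR and PFS are shown on both.

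The cost is a wording change, one extra table and slightly more work for the experts. They would work from the material they would have under the present wording, so no new readers, scans or masking procedure are needed. A fresh central image read, or masking to dose and adverse events, would be a larger undertaking and is not proposed.

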12.2 Analysis Populations

The full analysis population will comprise all patients who have been exposed to the trial drug. This population will be used for evaluation of all endpoints.

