12.3 Statistical Methods

The presentations will be done separately for the Dose Escalation part and the Cohort Expansion part.

In the reporting of the Dose Escalation part tables will report by cohort, while in the Cohort Expansion part tables will report by indication.

The shift from the 3q4wk dosing to the once q3wk dosing in the Cohort Expansion part may lead to a need for reporting some tables by dosing schedule. This will be described as appropriate in the SAP.

No formal statistical tests will be performed.

For efficacy analyses, the quartile estimates of PFS and DoR from the Kaplan-Meier product limit algorithm will be presented (Kaplan and Meier, 1958). The 2-sided 95% confidence interval will be presented as well. The number of events may be small, and thereby limit use of the Kaplan-Meier method to provide reliable information. In this case, descriptive statistics (e.g., n, mean, standard deviation, median, minimum and maximum) for PFS or DoR will be presented. Objective response (CR or PR) rate will be determined along with the corresponding 2-sided 95% exact binomial confidence interval.

All data will be listed. Baseline is defined as the latest available measurement made before the first treatment with tisotumab vedotin (HuMax-TF-ADC).

A patient will be considered as having completed the trial when all planned trial visits have been performed.

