12.5.3.3 Progression-free Survival

Progression-free survival is defined as the number of days from Day 1 in Cycle 1 to first PD or death. Progression-free survival will be derived for all patients and presented graphically as well as summarized using survival analysis methods.

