12.5.3.5 Patients without Disease Progression after Four Cycles

Percent of patients without PD after four cycles will be summarized.

12.5.4 Changes in Biomarkers, Including PSA and CA 125

Biomarkers, PSA, CA 125, soluble TF, etc. will be presented graphically: individual patient plots over time.

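### The response section labels Not Evaluable patients as disease progression, against the protocol's own definition of PD, and the label can inflate progression in the four-cycle summary

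*Protocol*

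**What the plan says.** Protocol Section 12.5.3.2 gives each patient one of five response categories: CR (1), PR (2), SD (3), PD (4) or Not Evaluable (5). Three statements then group them:

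- "Patients in response categories 1 and 2 are considered responders".
- "patients in response categories 4 and 5 are considered as failing to respond to treatment (disease progression"), where the words in brackets are a gloss on failing to respond.
- "Patients in response categories 1, 2 and 3 are considered to be in disease control".

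The planned response output is listed in the same section: "summaries of objective response, best overall tumor response and disease control will be presented by dose cohort and total". Section 12.3 adds that "Objective response (CR or PR) rate will be determined along with the corresponding 2-sided 95% exact binomial confidence interval". Section 12.2 defines one population, all exposed patients, and says "This population will be used for evaluation of all endpoints".

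Two other summaries depend on what counts as progression. PFS (Section 12.5.3.3) runs from Day 1 of Cycle 1 "to first PD or death". Section 12.5.3.5, whose heading refers to patients without disease progression, says only that "Percent of patients without PD after four cycles will be summarized". It does not say how Not Evaluable patients count.

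**The concern.** A patient is Not Evaluable when the available assessments do not support any of the other four categories. That is an absence of information about the tumour, and the bracketed label turns it into a statement that the tumour grew.

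The label matters because Section 12.5.3.1 says response is evaluated after four cycles as well as best overall, so the five categories, with their grouping, exist at the same time point as the summary in Section 12.5.3.5. An analyst looking for a rule on Not Evaluable patients there finds only one statement in the protocol, and it classes them under disease progression. The four-cycle figure would then count them as progressed while PFS, in the same patients, would not. Some of these patients may have stopped early for toxicity, and the report would show them as tumour progressions.

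**Working it through.** The plan attaches no figure to this rule, so there is none to reproduce. The check has two parts.

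**1. The label against the protocol's other definitions**

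- Section 12.5.3.1, Table 10: PD needs at least 20% and 5 mm growth in the target-lesion sum, new lesions, or unequivocal non-target progression. For prostate cancer with bone scan as the sole indicator, it needs at least two new lesions. A Not Evaluable patient has met none of these.
- Section 12.5.3.1, best overall response: patients who stop because of global deterioration without objective PD are kept apart as symptomatic deterioration, and objective progression is still to be sought. The label in 12.5.3.2 removes that separation.
- Sections 12.5.3.3 and 12.5.3.4: the events for PFS and duration of response are PD or death. Not Evaluable is not an event.

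The label can also fall on a patient whose scan shows no growth. SD requires the criteria to be met for at least six weeks (± 7 days) after first treatment. Take a Cohort Expansion patient who leaves at week 4 (28 days, below the 35-day lower limit) with an End of Trial CT that shows no change. This patient is not CR, PR or PD and cannot be SD. Only Not Evaluable remains, and Section 12.5.3.2 then glosses it as progression.

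**2. Size**

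Inputs: N = 20 and N = 30, the planned range for the Cohort Expansion part. Assumed, not from the protocol: 20% CR or PR, 40% SD, and 1 to 6 Not Evaluable (NE) patients taken from the remaining 40%.

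- Progressed, literal label = (PD + NE)/N
- Progressed, documented = PD/N
- Excess = NE/N

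| N | NE | PD | Literal | Documented | Excess (points) |
|---|---|---|---|---|---|
| 30 | 1 | 11 | 40.0% | 36.7% | 3.3 |
| 30 | 2 | 10 | 40.0% | 33.3% | 6.7 |
| 30 | 3 | 9 | 40.0% | 30.0% | 10.0 |
| 30 | 6 | 6 | 40.0% | 20.0% | 20.0 |
| 20 | 1 | 7 | 40.0% | 35.0% | 5.0 |
| 20 | 2 | 6 | 40.0% | 30.0% | 10.0 |
| 20 | 3 | 5 | 40.0% | 25.0% | 15.0 |
| 20 | 6 | 2 | 40.0% | 10.0% | 30.0 |

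The excess depends only on NE/N, not on the assumed response and SD rates.

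Quantities that do not move:

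- Objective response rate = (CR + PR)/N = 6/30 = 20.0% (exact 95% CI 7.7% to 38.6%), or 4/20 = 20.0% (5.7% to 43.7%), in every row.
- Disease control = (CR + PR + SD)/N = 18/30 = 12/20 = 60.0% in every row.
- Categories 1-3 plus categories 4-5 = 18 + 12 = 30, or 12 + 8 = 20, so this split covers every patient.

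The opposite error is also possible. With 3 NE of 30, treating everyone not documented as PD as free of PD gives (30 − 9)/30 = 70.0%, although only 18/30 = 60.0% were shown to be so.

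**The case against.** The strongest reply is that the sentence only groups categories 4 and 5 as treatment failures and does not recode Not Evaluable as PD. The two stay separate categories, PD has its own definition, and both the PFS section and the operative sentence of 12.5.3.5 use the term PD. On that reading the two summaries share one event, and the inflation arises only if the bracketed words are carried from one section into another. The protocol also leaves detailed methods to the SAP (Section 12.1), and early toxicity stops are not automatically Not Evaluable: CT is scheduled at the End of Trial visit in both parts, and Dose Escalation patients who stop treatment have follow-up visits with CT.

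Most of this stands. The miscount is conditional, its counts are assumed, and a landmark rule for Not Evaluable patients could properly sit in the SAP. What remains is that the protocol does not stay silent: it states a label that its own definitions contradict, and the heading of 12.5.3.5 uses the same term as the label.

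Three stronger readings are tempting and not supported:

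- A reader might infer that SD is unclassified, because it is neither responder nor failure. The next sentence places it in disease control, categories 4-5 are the exact complement of 1-3, and no planned summary needs responders plus failures to equal all patients.
- A reader might infer that PFS or duration of response is miscounted. Both are defined on PD or death.
- A reader might infer that the tolerability result is contaminated. The primary endpoint is adverse event incidence, which this sentence does not touch.

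**Conclusion.** The label is wrong as written: it conflicts with the PD definition and with the separate symptomatic-deterioration class, both in Section 12.5.3.1. Its effect on results is confined to the four-cycle summary and depends on reading the label literally there. On that reading, progression is overstated by exactly the Not Evaluable share: 3.3 to 20 points for 1 to 6 of 30, and 5 to 30 points for 1 to 6 of 20. Those counts are assumptions, since the protocol gives no expected number. Because Cohort Expansion tables are reported by indication, the share per patient is larger within an arm: 30 patients split equally over three arms (also assumed) gives 10 per arm, so one patient is 1/10, or 10 points. This is a minor wording flaw, worth correcting because the correction is so cheap.

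**What to change.** In Section 12.5.3.2, delete the bracketed words after the statement on categories 4 and 5. State that patients in these categories are non-responders and not in disease control, and that only documented PD (or death, where the endpoint includes it) counts as progression.

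In Section 12.5.3.5, report three rows over all exposed patients: documented PD, documented without PD, and Not Evaluable. Not Evaluable patients then count neither as progressed nor as progression-free. Restricting progression to documented PD without the third row would not be enough, because unevaluated patients would by default be counted as free of PD.

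The cost is a few sentences in the protocol and one extra table row. Data collection, the analysis population and the other endpoints stay as they are.

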12.5.3.3 Progression-free Survival

Progression-free survival is defined as the number of days from Day 1 in Cycle 1 to first PD or death. Progression-free survival will be derived for all patients and presented graphically as well as summarized using survival analysis methods.

12.5.3.4 Duration of Response

Duration of response is defined as the number of days from the first documentation of objective tumor response (CR or PR) to the date of first PD or death.

12.5.3.5 Patients without Disease Progression after Four Cycles

Percent of patients without PD after four cycles will be summarized.

12.5.4 Changes in Biomarkers, Including PSA and CA 125

Biomarkers, PSA, CA 125, soluble TF, etc. will be presented graphically: individual patient plots over time.

